The AcTIVE-CBT treatment involves eight 60-minute treatment sessions spaced over 3 months, delivered via clinical video telehealth methods by clinical psychologists to Veterans in their homes. Psychologists will refer to Fitbit output during the initial evaluation and each treatment session, including reminders and tips about Fitbit use, evaluating step count homework, and tracking overall progress towards goals; the protocol for AcTIVE-CBT is provided as Attachment KK – AcTIVE-CBT Workbook. The TBSCE treatment involves an initial 60-minute telephone education session by a psychologist including education on CBT principles; the provision of an educational book for CBT self-management ('Managing Pain Before It Manages You' by Margaret A. Caudill PhD) and orientation to the workbook;⁴³ and a structured plan for weekly reading and homework using the workbook⁴³. The content of TBSCE interactions in the one initial 60-minute session is as per Attachment MM, but can be adapted to follow psychologists' typical practices for patients beginning CBT for pain who are interested in the treatment but are unable to continue with further sessions. In addition, the psychologist providing TBSCE will contact the participant at the approximate midpoint of the 3-month follow-up period to reinforce key concepts as needed, encourage continued participant-directed use of the plan for weekly reading and workbook use, and answer questions. The psychologist will also be available by phone to address any areas of concern or participant questions during follow-up. TBSCE represents a focused yet 'active' treatment beyond what is normally provided after LRFA. Around the time of the start of behavioral treatments for participants in both the AcTIVE-CBT and TBSCE arms, research staff will provide a written summary of certain data elements from Visit 0 and 1, reflecting the same type of information that would be obtained during an initial clinical evaluation for CBT. This written information will be shared in the form of Attachment NN ('Brief Summary Baseline Data' form). The purpose of this is to provide information to the therapist that will be useful in understanding the participant's baseline status and thus providing effective clinical care. These data elements will include report of pain intensity, number of pain locations, treatment expectancy, hours missed from work or volunteer activities, CLBP-related functional limitations, and past treatments for CLBP. The Brief Summary Baseline Data form (Attachment NN) will be generated by research staff and sent to the clinical therapist using the secure VHA Privacy Act/HIPAA Envelope or fax or encrypted email. If a fax is sent, once the fax receipt has been confirmed at the destination location (confirmed by the therapist), the original form will be destroyed via placement in a designated shredding bin (by the research staff member). If the therapist is located at Seattle campus, the research staff can come to the clinical area for a direct handoff of the Brief Summary Baseline Data form. Once the form is handed to the clinical therapist, the therapist can review this information and record whatever information they would normally do as per their usual clinical practice, in the medical record. The clinical therapist will then destroy the form via placement in a designated shredding bin, not retaining the record for future use, so as to limit potential risk for privacy issues.

In order to avoid imparting biases regarding which treatment is the 'intervention' and which the 'control', AcTIVE-CBT is referred to as 'extended CBT' in the Informed Consent documents and all discussions with the patient, and TBSCE treatment is referred to as 'brief CBT' in the Informed Consent documents and all discussions with the participant.

The AcTIVE CBT and TBSCE control conditions will both be delivered by licensed Clinical Psychologists with specific expertise in cognitive-behavioral therapy and its application to the treatment of chronic pain. Both treating psychologists have appointments within Rehabilitation Care Services at VAPSHCS and are approved for clinical telehealth service modalities. Both study psychologists will be instructed by [name] in the aspects of clinical CBT treatment to be provided for participants in this study, but are considered clinical staff providing standard-of-care clinical services for chronic pain, and thus not actively engaged in the research procedures. Participants receiving a given treatment (AcTIVE CBT or TBSCE) will generally receive the same information; however, we expect some variation in the amount of time spent on each topic and the specific language used to convey materials. As per usual clinical practice, psychologists will tailor the information in whatever way is indicated to ensure understanding of the content, and to provide individualized support based on personalized goals, barriers, and abilities. If patients specifically request to have one or more in-person sessions of either AcTIVE-CBT or TBSCE in lieu of video telehealth or telephone (respectively), therapists will accommodate such requests as their clinical schedules and availability allow.

ACTIVE-CBT

Psychologists providing the AcTIVE-CBT intervention will receive reports on a participant's Fitbit output and compliance in advance of each treatment session. We will strive to schedule the AcTIVE-CBT sessions at consistent days/times within the week if possible, to facilitate routine and attendance. We will also attempt to schedule sessions evenly across the 3-month follow-up period, to ensure adequate practice time for patients between sessions. ACTIVE-CBT sessions will generally begin with a review of the Fitbit-related output provided by research staff, to gauge activity since the prior session. Sessions will typically include activity plans, expectations, and goals for the next session and long-term. The schedule, scope, and content of treatment as part of the AcTIVE-CBT are similar in scope and content to typical CBT for chronic pain as provided in the RCS service line, but have been specifically tailored for low back pain based on the results of recent successful RCT.^{3,4} Some key differences between AcTIVE-CBT and the standard video-based CBT treatment available at VAPSHCS include a greater focus on encouraging walking and physical activity, using the Fitbit Zip units, and greater emphasis on understanding flare-ups and relapse prevention. The components of AcTIVE-CBT are presented in Table 1 below and details of the treatments are found in the patient workbook (Attachment KK – AcTIVE-CBT Workbook). Please note that patient workbook is distinct from the therapist/psychologist manual (Attachment JJ – AcTIVE-CBT Manual). AcTIVE-CBT is meant to be responsive to clinical needs and realities, and if needed, the timing, order, and intensity of these components may vary slightly depending on the specifics of the individual participant, but all will be covered during the 3-month treatment period. AcTIVE-CBT may include audio content. These materials were previously submitted to the IRB with the initial submission. This audio content can be provided to participants in CD format and/or by accessing the content on the VA Seattle ERIC website. The audio content is not copyrighted and we have obtained permission from the audio content creators to use the content without restriction. We have also obtained permissions from the

VAPSHCS privacy officer ([name]), information systems security officer ([name]), area manager for end user operations for IT ([name]) (see correspondence submitted, including also the IRB Director [[name]]).

TBSCE

Participants in the TBSCE arm will also receive the Fitbit Zip units, but education and treatment will not be specifically structured around the Fitbit. TBSCE will begin with a 60-minute educational session by a rehabilitation psychologist conducted over the telephone. It will be followed by one brief phone call (10-20) minutes in length) from the rehabilitation psychologist to the participant between 1-2 months after the initial TBSCE session. TBSCE steps follow the structured CBT program included in the book "Managing Pain Before It Manages You" by Caudill, supplemented by a workbook that we have developed for TBSCE. The Caudill book taken together with the workbook are sufficiently detailed that a participant can independently learn the concepts and complete exercises. The workbook includes many of the same topics covered in the AcTIVE-CBT treatment, but in a different order, and without a specific focus on physical activity. Participants will be encouraged to set weekly goals for working through the sessions in the book and completing the assigned readings. At the introductory phone consultation, psychologists will advise participants in setting up a specific written schedule for completing the workbook sections and activities over the 3-month period that the participant will record in their treatment manual (with specific dates when completion of content for a session is expected to be completed). Long-term activity goals and weekly activity goals will be discussed, and these will also be recorded by the patient in the patient treatment manual (Attachment LL – TBSCE Manual (Instructions)). Weekly workbook homework will include: 1) education on chronic pain, 2) theories of pain and diaphragmatic breathing, 3) progressive muscle relaxation and visual imagery, 4) automatic thoughts and pain, 5) cognitive restructuring, 6) stress management, 7) time-based pacing, 8) pleasant activity scheduling, 9) anger management, 10) sleep hygiene, and 11) relapse prevention and flare-up planning.

We may make non-substantive changes to AcTIVE-CBT and TBSCE manuals, workbooks, and provider scripts as the study proceeds. Any substantive changes will be submitted to the IRB for further review.

Quality Assurance

After each session of AcTIVE-CBT, therapists will complete a brief checklist to document the content areas covered in each session (see Attachment OO). These checklists will be used to assess the quality of the AcTIVE-CBT treatment and that major content areas have been covered. Checklists will be retained in a locked file cabinet in the therapist's locked treatment room/office until the last treatment session is completed. After the last treatment session is completed, the therapist will send the checklist to research staff using the secure VHA Privacy Act/HIPAA Envelope or fax or encrypted email. If a fax is sent, once the fax receipt has been confirmed at the destination location (confirmed by discussion or email with research staff), the original checklist will be destroyed via placement in a designated shredding bin (by the therapist). If the therapist is located at Seattle campus, the research staff can come to the clinical area for a direct handoff of the checklist.

Checklists will be collected by research staff and used to track treatment quality/content covered for each participant. These checklists will be treated in the same manner as study questionnaires, using the same methods for data security.

Table 1: Overvi	ew of Content in AcTIVE-CBT and TBSC	E treatments*
	AcTIVE-CBT	TBSCE
General descriptions and content prior to first session with psychologist	All sessions conducted by video telehealth and psychologist-delivered. Participant will receive basic instruction on Fitbit Zip use from research staff prior to randomization. Participant will receive ongoing research staff support regarding Fitbit use post- randomization, including telephone contacts by research staff at approximately 2 weeks, 6 weeks, and 10 weeks post-randomization.	TBSCE is an active yet lower-dose intensity treatment as compared to AcTIVE-CBT. TBSCE will include pain education and CBT-related education and guidance through [name] CBT ' Managing Chronic Pain ' workbook (referred to as '' Caudill' below) Participant will receive basic instruction on Fitbit Zip use from research staff prior to randomization. Participant will receive ongoing research staff support regarding Fitbit use post-
	Research staff will produce regular reports on participant Fitbit output and compliance prior to each treatment session, which will be made available to the psychologist and the data relayed to participants during the treatment sessions.	randomization including telephone contacts by research staff at approximately 2 weeks, 6 weeks, and 10 weeks post-randomization.
Session 1	Welcome and Introductions; Pain and the Brain 60 min. session by rehabilitation psychologist	 Welcome and Introduction; Introduction to Materials (TBSCE Manual and 'Managing Pain Before It Manages You' workbook by Caudill); Overview of the Treatment Structure; Questions Reading Assignments Chapter 1 (Beginning to Take Control of Your Pain) Chapter 2 (Understanding Pain) Topics: Education about different types of pain Self-assessment about how you currently cope with pain. 60 min. telephone session by rehabilitation psychologist
Session 2	Getting Active! Goal-Setting, Pacing, and Managing Flare-Ups 60 min. session by rehabilitation psychologist.	Reading Assignments • Chapter 3 (The Mind-Body Connection) Topics: • Pain as a form of Chronic Stress • Relaxation Response
Session 3	Thoughts, Feelings, and Pain 60 min. session by rehabilitation psychologist	 Reading Assignments Chapter 4 (The Body-Mind Connection) Topics: Increasing activities How doing activity improves your mood Pleasant activities
Session 4	Challenging Automatic Thoughts: Part I	Reading Assignments:

enging Automatic Thoughts: Part II n. session by rehabilitation hologist ing about Thoughts: Review and le-Shooting	 Reading Assignments: Chapter 5 (The Power of the Mind). Topics: How to use powerful cognitive techniques to change your mood. Recognize your "self-talk", or "automatic thoughts" Recognize thought distortions 10-20 min psychologist contact by phone conducted between 1-2 months after the initial TBSCE session, to encourage progress with written materials and self-directed progression. Reading Assignments:
n. session by rehabilitation nologist	Chapter 6 (Adopting Healthy Attitudes) Topics: • Health attitudes
Beliefs and Behaviors: Skill Review leep 60 min. session by ilitation psychologist	Reading Assignments: Chapter 8 (Effective Communication) Topics: • Assertiveness • Active Listening
aining Gains and Coping with cks 60 min. session by ilitation psychologist	 Reading Assignments: Chapter 9 (Effective Problem Solving) Chapter 10 (The End of The Beginning) Topics: Setting Goals Applying your coping skills to problems Relapse Prevention Coping with Pain During Flare-Ups
	leep 60 min. session by ilitation psychologist aining Gains and Coping with cks 60 min. session by

the changes made are substantive.

Blinding Strategy:

Blinding with respect to the lumbar procedures (LRFA vs. simulated LRFA):

- 1. Participants and treating interventional spine providers will be blinded to the status of LRFA vs. simulated LRFA. The PI [name] and [name] will not be blinded, since they are the overseeing study clinicians. Further details are provided below in Table 2.
- 2. For blinding purposes, both LRFA and simulated LRFA will be performed in an identical fashion with the exception of medial branch lesioning, which will not be done in the simulated LRFA group, as described above. Duration and sounds of both the LRFA and simulated LRFA procedures will be similar. Both LRFA and simulated LRFA will apply all safety precautions normally used in our facility such as not using general anesthesia, and the use of both sensory and motor stimulation to avoid incorrect electrode placement (described further below).
- 3. During the procedure (LRFA or simulated LRFA), the treating interventional spine provider will make initial placements of all LRFA electrodes to be used in that procedure as he/she would do normally for LRFA. Once the treating interventional spine provider has placed all LRFA electrodes, the treating interventional spine provider will leave the room and subsequently remain blinded to the procedure allocation (i.e. the randomization to LRFA vs. simulated LRFA). The 2nd interventional spine attending physician will take over the procedure once the treating interventional spine provider leaves the room; the 2nd interventional spine attending physician will *not* be blinded to the procedure allocation. After the treating interventional spine provider leaves the room, the 2nd interventional spine attending physician will either use the radiofrequency machine in the appropriate manner for standard LRFA by lesioning the nerve, or administer the therapeutic MBB (for the control procedure) and apply the simulated LRFA lesion. During simulated LRFA, a recording will be played (Attachment X -Simulated LRFA Recording), by either the 2nd interventional spine attending physician or the clinical assistant, to simulate the typical sounds of LRFA. Additionally, the 2nd interventional spine attending physician will turn on sensory stimulation for a short period of at least 3 seconds towards the end of each simulated lesion time, maintaining stimulation intensity no higher than the level where sensory input was initially noted by the patient during testing. The 2nd interventional spine attending physician will then make a slight repositioning of the LRFA needle to a 2nd location, and administer the 2nd lesion (or the simulated 2nd lesion). If the simulated LRFA procedure is performed, the 2nd interventional spine attending physician or clinical assistant will turn on the audio recording of the LRFA at any times that the lesioning of the nerves would normally occur. Additionally, the 2nd interventional spine attending physician will again turn on sensory stimulation for a short period of at least 3 seconds towards the end of each simulated lesion time, maintaining stimulation intensity no higher than the level where sensory input was initially noted by the patient during testing.
- 4. The patient and the treating interventional spine provider are therefore blinded to the procedural treatment received. We will employ several strategies to ensure patients are not able to determine which intervention they receive based on the sounds and length of the procedure:
 - i. We will enroll only patients who have not had prior LRFA
 - ii. The electrode will remain in place for the full 90 seconds (and repositioned to simulate a second lesion) for each simulated lesion site.
 - iii. We will use a pre-recorded audio recording of an LRFA procedure in order to simulate the sounds made by the machine during the ablation. We will pre-test this recording several times in the pain clinic in advance of the first randomization.
 - iv. We will use a brief period of sensory stimulation during the simulated LRFA lesion as described above.
- 5. In some clinical situations, it may be impossible for a 2nd interventional spine attending to be on hand to complete a LRFA or simulated LRFA procedure, and maintain blinding of the treating interventional spine provider. For instance, a clinical situation may call that provider away or detain

that individual. In such an instance, the treating interventional spine provider will become unblinded.

6. In the event that participants who are randomized to LRFA vs. simulated LRFA subsequently wish to go on to receive the treatment they were not randomized to, or wish to go on to another lumbar-related procedure that for some reason necessitates that the participant become unblinded to the treatment they were randomized to, prior to the end of the 3-month main follow-up period of data collection, we will unblind participants to their treatment status. This will be done by informing the treating interventional spine provider of the procedural treatment received (LRFA vs. simulated LRFA) prior to a clinical appointment with the participant. The Veteran participant and their provider will then have the information needed to confer and make a fully informed decision about the next clinical treatment steps that are most appropriate for the Veteran.

Blinding with respect to CBT treatments (AcTIVE-CBT vs. TBSCE):

7. It is not possible to blind patients and rehabilitation psychologists to whether or not they are receiving AcTIVE-CBT or TBSCE. To limit the potential for influencing participants' perceptions of the interventions as more or less likely to be effective, participants will not be specifically told which of the AcTIVE-CBT or TBSCE treatments represents the intervention of interest or the control treatment in the current study. They will however have full advance knowledge of what the treatments will actually entail.

Table 2: Blinding Status of Research Staff		
	Blinded/Unblinded and Reason	When blinded
[name] (PI)	Not blinded (main study physician responsible for clinical issues)	N/A
[name]	Not blinded (study physician responsible for clinical issues pertaining to mental health)	N/A
Drs. [name], [name], [name]	Yes; blinded when not acting as the 2 nd interventional spine attending physician (which he/she will be in cases when another spine provider is the treating interventional spine provider ^a)	Entire study, see superscript 'a' to the left
[name]	Not blinded; except when he is acting as the treating interventional spine provider (in which instances he will be blinded ^b)	Entire study⁵
[name]	Blinded and no contact with individual-level study data at any point	Entire study

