The randomization process involves:

- 1. Treatment assignments will be stored centrally electronically in a secure database at VAPSHCS. Envelopes containing the treatment assignments (hardcopies) will also be pre-generated.
- 2. We will utilize computer-generated permuted-block randomization to achieve roughly balanced groups. We will use random blocks that are not divulged to the research staff involved in recruitment in order to avoid bias in the recruitment process. Randomization will be stratified by MBB block responses (50-79% vs. ≥80%).
- 3. Reminder emails will be sent to the clinical assistant ([name]) and the 2nd interventional spine attending physician the day before the scheduled procedure to remind them that they will need to obtain the randomization allocation on the day of the procedure, prior to the procedure. The 2nd interventional spine attending physician is the second interventional spine attending physician-other than the treating spine provider, who will be in the room during LRFA or simulated LRFA and take part in these procedures. Similar emails will be sent on the morning of the procedure.
- 4. Prior to the lumbar procedure, the clinical assistant and the 2nd interventional spine attending physician will open the envelopes which reveal the procedural and behavioral treatment allocations. A non-blinded research staff member will be present to facilitate this and be aware of the treatment allocations. These assignments contained in the envelopes will direct the 2nd interventional spine attending physician whether to perform a standard LRFA or the simulated LRFA, and whether the participant will receive AcTIVE-CBT or TBSCE. A primary function of the clinical assistant is to make sure that the 2nd interventional spine attending physician knows and performs the allocated treatment on the day of the procedure.

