 - If a study participant is unable to use the Fitbit Zips, they will be categorized as 'non-Fitbitcompliant'. They will be able to continue in the study, but the randomization will be stratified by 'Fitbit-compliant' vs. 'non-Fitbit-compliant' status.

Those ineligible for the study, those who decline to participate, and those who participate but later are deemed ineligible and are not randomized (i.e. those who fail the run-in period) will continue to be seen in the VAPSHCS Pain Clinic and will continue to receive appropriate care for CLBP, which may include LRFA or cognitive behavioral therapy (CBT) for pain for appropriate patients.

Usual Care for MBBs and LRFA at VAPSHCS:

Usual practice in the VAPSHCS Pain Clinic involves screening patients with CLBP for LRFA eligibility with 2 separate sets of MBBs. This is done because the temporary pain relief that happens with MBBs (temporary anesthetic blocks of the 'medial branch nerves') simulates the type of pain relief that should occur with LRFA (when the nerves are ablated [destroyed]). At VAPSHCS these 2 sets of MBBs are scheduled, on average, about 3 weeks apart. Individuals who have 'positive' responses to MBBs (temporary resolution or marked improvement of CLBP) on both occasions, and meet other clinical criteria, are eligible for LRFA. Those who do not have positive responses to MBBs, or do not meet other clinical criteria, are not eligible for having LRFA because they will not benefit from the procedure. 2 sets of screening MBBs are the highest standard of care for selected LRFA candidates in the US because up to 50% of patients who have positive responses to 1 set of screening MBBs are having 'false positive' responses and would not respond to LRFA. The performance of MBBs in usual clinical practice always requires fluoroscopy (x-rays) to position the spinal needles in the appropriate locations; fluoroscopy is always needed for LRFA for the same reason in usual

clinical practice. At VAPSHCS, LRFA is typically scheduled for a time within 3 weeks after the 2nd set of MBBs.

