	End of the duration of pain relief is marked by the point where the majority of the pre-block pain intensity levels (>50%) have returned. For instance, if a potential participant reports 6/10 pain pre-MBBs, and achieves 1/10 pain post-MBBs, pain relief would be considered to be ongoing at the point where pain intensity was reported as 3/10, but not at the point where pain intensity was reported as 4/10. Depending on the distribution of recruited participants' MBB responses (50-79% vs. ≥80%) after the initial period of recruitment, we may restrict study participation in the participant selection phase in order to oversample participants who have ≥80% relief with MBBs.		
Other follow-up assessments	Phone call 2-5 days after 1 st set of MBBs, to assess for return of typical low back pain, with or	Phone call 2-5 days after 2 nd set MBBs, to assess for return of typical low back pain, with or	

	without patient referring to their pain diary results. If a clinical phone call or other assessment has been made to assess MBB response by clinical staff or the treating interventional spine provider, the information from that assessment will be used instead of the phone call by study staff.	
Relief of pain	 ≥50% improvement in typical low back pain symptoms For both the 1st and 2nd set of MBBs, we will calculate % pain improvement based on patient reported pre-procedure 0-10 pain numeric rating scale score for typical low back pain, minus the post-procedure 0-10 pain numeric rating scale scores for typical low back pain, divided by the pre-procedure 0-10 pain numeric rating scale scores for typical low back pain the post-procedure for typical low back pain. Patients will be blinded to the thresholds of % improvement that define a 'positive response'. 	

A. Initial Screening: We will pre-arrange permission to approach patients with chronic low back pain presenting to the VAPSHCS system Pain Clinic, who meet the Initial Screening criteria from Table 4 (including but not limited to \geq 50% pain improvement with MBBs as performed in routine clinical practice in our institution). Patients who appear to meet Initial Screening criteria will be approached to participate in this trial by research staff.

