The purpose of the run-in period is 1) to identify those participants who are able to use the Fitbit a minimum amount which we consider to be 'Fitbit-compliant', so that this variable can be adjusted for analytically, and 2) exclude participants who fail Final Screening criteria or who are determined to be highly unlikely to be able to participate in study procedures (i.e. those who cannot be contacted by phone or in-person at least one time during the run-in period, indicating that they would not be able to complete subsequent telephone questionnaires). During the run-in period, research staff will be available to receive phone calls or visits from the participants so as to help them with any Fitbit related questions they have, or their ability to sync their data. Once it seems that a participant is able to use the Fitbit and sync it (which in many cases may be immediately after Visit 1), the research staff will begin a "test period" of 7 days. The earliest possible start of a test period would be the day after the randomization. If a participant has not synced their Fitbit by day 3 or 4 of the test period, they will receive a telephone call from research staff to offer help and answer questions, and to remind the participant to sync the Fitbit. On days 5, 6, or 7, participants will receive up to one telephone contact/reminder and/or voicemail message left, in order to remind the participant to sync their Fitbit by the end of the 7th day after the start of the test period. If a life issue or barrier presents that interferes with ability to use the Fitbit unit, or the participant encounters a technological hurdle

of some type (such as device failure) the test period may be restarted at any time, and the process repeated. In addition, the test period can be extended as needed due to holidays or absences (either for the participant or research staff) on an ad hoc basis. However, if a full test period elapses without the participant syncing their Fitbit, this would constitute a failure of the run-in period.

- i. Research staff will monitor the frequency of participant Fitbit use, and whether they are able to periodically upload their data. Participants who do not use their Fitbit, or do not upload data at least once during the run-in period, will receive reminder phone calls.
- ii. Research staff will make telephone contacts as needed with participants to help participants learn how to use their Fitbits.

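### Sections 5.1 and 5.2 each name a different randomisation stratifier, no rule says which MBB value sets the stratum, and the Section 5.6 ANOVA includes neither factor (minor)

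*Combined protocol and SAP*

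**What the plan says.** **Allocation.** Section 5.1, under Randomization, specifies permuted blocks and adds "Randomization will be stratified by MBB block responses", with bands of 50-79% and ≥80%. Fitbit status is not mentioned there. The same list states "Envelopes containing the treatment assignments (hardcopies) will also be pre-generated"; the envelopes are opened on the day of the procedure. Section 5.2, Brief Overview of Recruitment, keeps a participant who cannot use the Fitbit in the study, "but the randomization will be stratified by" Fitbit-compliant versus non-compliant status. MBB response is not mentioned there.

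**Stratum membership.** Section 5.2, Table 3, says "For both the 1st and 2nd set of MBBs, we will calculate % pain improvement", so each participant has two values. Table 4 requires at least 50% on each set. Section 5.2 E lets the Fitbit run-in be waived for approach-letter recruits when time is short.

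**Analysis.** Section 5.2 C gives one reason for classifying Fitbit status: "so that this variable can be adjusted for analytically". Section 5.6 specifies a two-way ANOVA of 3-month RMDQ on LRFA, AcTIVE-CBT and their interaction. On adjustment, it says only that baseline imbalance will be examined and that the small sample limits what can be adjusted for. It gives effect magnitude and variability as what the pilot is meant to supply to a later trial.

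**The concern.** A stratified scheme needs three things on paper: the factors, the rule that puts each person in a stratum, and whether the analysis uses the strata. Here a reader cannot tell whether there are two strata (one factor) or four (both). A participant with 60% relief on the first MBB set and 90% on the second fits both MBB bands. With pre-generated envelopes, the practical risk is an allocation taken from the wrong list, and a scheme that cannot be reproduced afterwards.

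In the analysis, stratified blocks remove part of the between-arm variation due to the stratifier. A model without the stratifier still counts that variation as residual error, so its standard errors are too wide if the factor is prognostic. The run-in section expects adjustment for Fitbit status, and the analysis section does not carry it out.

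**Working it through.** **1. Plan's own figures.** 30 recruited − 10 lost = 20 completers, and 20/4 = 5 per cell. The two-way ANOVA with interaction has 20 − 4 = 16 residual df. There is no power calculation to reproduce.

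**2. Effect of leaving out one stratifier.** Let p be the share of participants in one stratum and d the stratifier's effect in within-stratum SDs. Both are assumptions. If the four cells are balanced on the factor, the expected residual variance without it is 1 + (20/16)·p(1−p)·d². The marginal (ordinary between-patient) variance is 1 + p(1−p)·d².

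| p | d | Residual variance | Marginal variance | Ratio |
|---|---|---|---|---|
| 0.2 | 0.5 | 1.05 | 1.04 | 1.01 |
| 0.5 | 0.5 | 1.08 | 1.06 | 1.01 |
| 0.2 | 1 | 1.20 | 1.16 | 1.03 |
| 0.5 | 1 | 1.31 | 1.25 | 1.05 |

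The third column is 5-31% above the within-stratum variance of 1. Against the marginal variance, the excess is only about 1-5%.

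**3. Standard error of the LRFA main effect.** With exact balance, the ratio of reported to true SE is the square root of the residual variance: √1.05 = 1.02 and √1.08 = 1.04 at d = 0.5; √1.20 = 1.10 and √1.31 = 1.14 at d = 1. Real strata leave blocks unfilled, so this was also simulated. The settings were 20 completers, permuted blocks of 4 or random 4/8 within strata (block sizes assumed), p from 0.2 to 0.5, 8,000 trials per setting and no true treatment effect. For one omitted factor, the reported SE was too wide by about 0% (d = 0), 2-4% (d = 0.5) and 6-11% (d = 1). Mean estimates were within about 0.01 SD of the truth in every setting, so there is no bias. The simulation treats the 20 completers as those randomised. Losses after randomisation would weaken the balance and so the discrepancy.

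**4. Sampling uncertainty for comparison.** The 95% limits for a variance on 16 df are 16/χ²(0.975; 16) = 0.55 and 16/χ²(0.025; 16) = 2.32 times the estimate.

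**5. Cost of adjusting when d = 0.** Main-effect variance rises by about 0.5-2% (one factor) or 2-6% (both). The t critical value goes from 2.120 (16 df) to 2.131 (15 df) or 2.145 (14 df). The interval half-width therefore grows by about √1.005 × 2.131/2.120 − 1 = 0.8% to √1.02 × 2.131/2.120 − 1 = 1.5% with one factor. With both, it grows by about √1.02 × 2.145/2.120 − 1 = 2.2% to √1.06 × 2.145/2.120 − 1 = 4.2%.

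**6. How often the two MBB values fall in different bands.** With share p at ≥80% on each set and correlation ρ between the band indicators, the discordant share is 2p(1−p)(1−ρ). For p = 0.5 and ρ = 0.2 this is 40%; for p = 0.8 and ρ = 0.8 it is 6.4%. That is about 1 to 8 of 20 participants. Both inputs are assumptions.

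**The case against.** The strongest reply is that little harm follows. Section 5.6 focuses on effect sizes rather than significance and disclaims power, the estimates are unbiased, and the SE error is conservative. Every non-zero figure rests on a prognostic effect that the documents do not supply. Section 5.6 also acknowledges that 20 completers leave little room to adjust. All of this stands and is why the point is minor. It does not remove the gap: the trial randomises within these groups, says it classifies one of them so as to adjust for it, and then states no decision.

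Several stronger readings are tempting but not supported:

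- *The two sections contradict each other.* Both factors could apply. The scheme is incomplete, not contradictory.
- *The pilot will hand the next trial an inflated SD.* Most of the 5-31% is real between-patient variance, which an unadjusted trial should plan on. The SD is too large only as input to a trial that itself stratifies and adjusts, and the documents do not say the future RCT will.
- *Waived recruits become non-compliant by default.* Section 5.2 C classifies wear during the test period, and a waived run-in has none. They are unassessed.
- *Low Fitbit users are both excluded and retained.* Section 5.2 C does say "if a full test period elapses without the participant syncing their Fitbit, this would constitute a failure of the run-in period", and Section 5.2 does not randomise "those who participate but later are deemed ineligible and are not randomized (i.e. those who fail the run-in period"). But Section 5.7 explains run-in failure as not being reachable, and the overview and item iv of Section 5.2 C likewise exclude on the run-in for non-contact. The sync sentence is the outlier.
- *Fitbit status is measured after randomisation.* One sentence in Section 5.2 C dates the earliest test period that way. The sentence before it says the period can begin once the participant can use the device, "which in many cases may be immediately after Visit 1", and the heading places the run-in between Visits 1 and 2. This is a slip.

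Section 5.2 also says that a restriction to ≥80% responders would affect both screening stages, which hints that both MBB sets count. It is not a stratum rule.

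**Conclusion.** The point holds as a minor one. The documents name two stratifiers in separate places without linking them, give no rule for which MBB value decides the stratum, and specify an ANOVA with neither factor despite the stated purpose of classifying Fitbit status. Treatment estimates are not biased. The measurable consequence is a main-effect SE that is too wide by about 2-4% if one omitted binary factor has an effect of 0.5 SD, or 6-11% at 1 SD, and not at all if it is not prognostic. The residual SD overstates the marginal SD by at most a few percent, small beside a variance interval of 0.55 to 2.32 times the estimate. These sizes assume 20 completers, stratum shares of 20-50% and blocks of 4 or 4/8. Figure 2 and the attachments were not available and may hold further detail on the scheme.

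**What to change.** **Main change, Section 5.6.** Add: *The 2-way ANOVA will include LRFA, AcTIVE-CBT, their interaction and the binary stratification factor(s) used in randomization; a factor with an empty or near-empty level will be dropped; the result without them will be shown beside it.* This respects the plan's small-sample caution because both results are reported. It takes residual df from 16 to 15 (one factor) or 14 (both), with the small precision loss shown above if the factors turn out not to be prognostic. If recruitment is later restricted to ≥80% MBB responders, the MBB factor would have little left to adjust for and could be dropped under the same rule.

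**Supporting clarifications, wording only:**

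1. State the same stratifier(s) in Sections 5.1 and 5.2, matched to the lists in use so that none has to be regenerated.
2. Name the MBB value that sets the stratum: first set, second set, or a stated combination.
3. If Fitbit status is a stratifier, say which list participants with a waived run-in are drawn from.
4. Reconcile the Section 5.2 C sentence on a test period without a sync with the rest of Section 5.2 and with Section 5.7, and correct the sentence that dates the test period from randomisation.
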